15.1.4 Serious Adverse Events

Serious adverse events (SAEs) are those events recorded as "Serious" on the Adverse Events page of the (e)CRF. A summary of serious TEAEs/AESIs by SOC and PT will be prepared.

Document: Document path and title

Template No.: RWI_TP_BIOS0013 Revision 2 Reference: RWI_WI_BIOS0015

Page 24 of 45

15.1.5 Adverse Events Leading to Death

TEAEs leading to Death are those events which are recorded as "Fatal" on the Adverse Events page of the (e)CRF. A summary of TEAEs/AESIs leading to death by SOC and PT will be prepared.

15.1.6 CTC Grading for Adverse Events

AEs will be graded using the Common Toxicity grading (CTC) system version 4.03 as defined in the following link:

https://evs.nci.nih.gov/ftp1/CTCAE/CTCAE 4.03/CTCAE 4.03 2010-06-

14 QuickReference 8.5x11.pdf

CTCAE Grade 0 will be assigned for all non-missing values not graded as 1 or higher. Grade 5 will not be used. For laboratory tests where grades are not defined by CTCAE version 4.03, results will be categorized as low/normal/high based on laboratory normal ranges, according to each center.

The following listings/summaries will be generated separately for hematology, and biochemistry tests:

 Listing of all laboratory data with values flagged to show the corresponding CTCAE version 4.03 grades if applicable and the classifications relative to the laboratory normal ranges

For laboratory tests where grades are defined by CTCAE version 4.03:

- Worst post-baseline CTCAE grade (regardless of the baseline status). Each participant will be counted only once for the worst grade observed post-baseline.
- Shift tables using CTCAE version 4.03 grades to compare baseline to the worst ontreatment value

For laboratory tests where grades are not defined by CTCAE version 4.03:

Shift tables using the low/normal/high/ (low and high) classification to compare baseline
to the worst on-treatment value. Definition of low and high worst post-treatment values
were considered as follows:

Document: Document path and title

Template No.: RWI_TP_BIOS0013 Revision 2 Reference: RWI_WI_BIOS0015

o For all post-baseline visits (including unscheduled visits), in cases where the laboratory result is outside the normality range (i.e. <LLN or >ULN), the greatest deviation from the normality range will be considered as the worst post-treatment value. That is, if the largest deviation from normality is <LLN, the patient will be considered as "Low". If the greatest deviation is >ULN, the patient will be classified as "High". Cases where all post-baseline visits results are within the normal range will be classified as "Normal".

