12.4.8 Safety endpoints

For all safety analyses, the Safety set will be used.

The overall observation period will be divided into two mutually exclusive segments:

- 1. Pre-treatment period: from day of participant's informed consent to the day before infusion of OAV101
- 2. On-treatment period: from day of infusion of OAV101 through to the last study visit.

Adverse events

Details of the summary of AEs for the primary endpoint are detailed in Section 12.4.

In addition, separate summaries will be provided for death and other significant TEAEs leading to discontinuation.

All AEs, deaths, and SAEs (including those from the pre-treatment period) will be listed and those collected during the pre-treatment period will be flagged.

Vital signs

Details of the summary of AEs for the primary endpoint are detailed in Section 12.4.

12-lead ECG

Details of the summary of 12-lead ECG (cardiac safety assessment) for the primary endpoint are detailed in Section 12.4

- 1. PR, QRS, QT, QTcF, and RR intervals will be obtained from 12-lead ECGs for each participant during the study. ECG data will be read and interpreted (locally).
- 2. Categorical Analysis of QT/QTc interval data based on the number of participants meeting or exceeding predefined limits in terms of absolute QT/QTc intervals or changes from baseline will be presented.

All ECG data will be summarized by visit/timepoint.

Clinical laboratory results

Details of the summary of clinical laboratory results for the primary endpoint are detailed in Section 12.4.

In addition, shift tables using the low/normal/high/ (low and high) classification will be used to compare baseline to the worst on-treatment value.

Grading of laboratory values will be assigned programmatically as per NCI CTCAE version 4.03. The calculation of CTCAE grades will be based on the observed laboratory values only, clinical assessments will not be taken into account.

CTCAE Grade 0 will be assigned for all non-missing values not graded as 1 or higher. Grade 5 will not be used.

For laboratory tests where grades are not defined by CTCAE version 4.03, results will be categorized as low/normal/high based on laboratory normal ranges.

The following listings/summaries will be generated separately for hematology, and biochemistry tests:

• Listing of all laboratory data with values flagged to show the corresponding CTCAE version 4.03 grades if applicable and the classifications relative to the laboratory normal ranges

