For laboratory tests where grades are defined by CTCAE version 4.03:

- Worst post-baseline CTCAE grade (regardless of the baseline status). Each participant will be counted only once for the worst grade observed post-baseline.
- Shift tables using CTCAE version 4.03 grades to compare baseline to the worst ontreatment value

[figure not shown]
For laboratory tests where grades are not defined by CTCAE version 4.03:

• Shift tables using the low/normal/high/ (low and high) classification to compare baseline to the worst on-treatment value.

Other safety evaluations

Details of the summary of echocardiogram (cardiac safety assessment) for the primary endpoint are detailed in Section 12.4.

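### The SAP's worst-value rule can never fill the low-and-high shift category that both documents specify for ungraded laboratory tests, and it leaves the deviation scale undefined

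*SAP*

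**What the plan says.** Protocol 12.4.8 names the classification twice. For clinical laboratory results in general, "shift tables using the low/normal/high/ (low and high) classification will be used to compare baseline to the worst on-treatment value". The list for tests without CTCAE grades repeats it: "Shift tables using the low/normal/high/ (low and high) classification to compare baseline to the worst on-treatment value".

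SAP 15.1.6 carries the same four-way classification for ungraded tests ("Shift tables using the low/normal/high/ (low and high) classification to compare baseline"). A sub-bullet there defines the worst value over all post-baseline visits, unscheduled ones included: "the greatest deviation from the normality range will be considered as the worst post-treatment value". It gives three outcomes:

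- Low, when the child's largest departure lies under LLN.
- High, when it lies over ULN.
- Normal, when nothing after baseline is out of range.

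No fourth outcome follows. The sub-bullet does not say whether deviation is measured in absolute units, as a percentage of the limit, or as a fold change. SAP 4.3 records no change to the analysis from the protocol.

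**The concern.** Change in clinical laboratory results is among the primary safety endpoints (Protocol 12.4.1, SAP 15.1). For ungraded tests this shift table is the only worst-value tabulation that the SAP text names. The other tabulated outputs do not replace it. Change from baseline is summarised by scheduled visit, so opposite excursions in one child are not brought together. The incidence table for abnormal values in SAP 15.3 is limited to those that led to an adverse event.

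A child who falls below range at one visit and rises above it at another is the case that the fourth category exists to show. Under the SAP rule that child appears as Low or as High, and the other shift drops out of the table. Because the scale is not given, two programmers could follow the text faithfully and report opposite directions for the same child.

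**Working it through.** **Step 1: categories against outcomes.** Classify a child by whether any post-baseline value lies below LLN and whether any lies above ULN.

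| Any < LLN | Any > ULN | Category named | SAP rule returns |
|---|---|---|---|
| no | no | Normal | Normal |
| yes | no | Low | Low |
| no | yes | High | High |
| yes | yes | Low and high | Low or High |

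Three rows agree. The fourth cannot, whatever the data.

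**Step 2: does the scale matter?** Let x be the child's lowest value and y the highest. The deviations compared are:

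- absolute: LLN − x against y − ULN
- percent: (LLN − x)/LLN against (y − ULN)/ULN
- fold: LLN/x against y/ULN

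Take an illustrative range of 20 to 80 and x = 10 (0.5 × LLN).

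| y | Absolute | Percent | Fold |
|---|---|---|---|
| 96 (1.2 × ULN) | 10 v 16: High | 50% v 20%: Low | 2.0 v 1.2: Low |
| 120 (1.5 × ULN) | 10 v 40: High | 50% v 50%: tie | 2.0 v 1.5: Low |
| 152 (1.9 × ULN) | 10 v 72: High | 50% v 90%: High | 2.0 v 1.9: Low |

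The same results give different labels. The tie in the second row also shows that the SAP has no tie rule.

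**Step 3: how many children could be affected?** Protocol Table 8-1 schedules v = 11 post-baseline chemistry visits (Weeks 1, 2, 3, 4, 6, 8, 10, 12, 26, 52 and 78). Protocol 12.7.1 expects about 15 participants. The documents do not give the probability t that a value falls outside one limit, so t is an assumption, shown as a range. With independent visits and equal tails,

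P(both) = 1 − 2(1 − t)^v + (1 − 2t)^v.

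- t = 2.5%: 1 − 2(0.7569) + 0.5688 = 0.055, or 0.8 of 15 children
- t = 5%: 1 − 2(0.5688) + 0.3138 = 0.176, or 2.6 of 15
- t = 10%: 1 − 2(0.3138) + 0.0859 = 0.458, or 6.9 of 15

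These are per test. The SAP rule reports 0 in each case. Real visits are correlated within a child, so the figures indicate scale only and are not forecasts.

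**Step 4: does the rule lean one way?** The setup was 200,000 simulated children, 11 independent visits, and limits that leave 2.5% in each tail. Among children abnormal in both directions, the proportion labelled High was:

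| Values | Absolute | Percent | Fold |
|---|---|---|---|
| Lognormal, SD of log 0.1 / 0.3 / 0.6 | 0.62 / 0.80 / 0.94 | 0.51 / 0.54 / 0.56 | 0.50 / 0.50 / 0.49 |
| Normal, CV 2% / 10% / 25% | 0.51 / 0.50 / 0.49 | 0.49 / 0.40 / 0.24 | 0.48 / 0.38 / 0.22 |

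The lean to High is strong only for right-skewed values on an absolute scale. Elsewhere it is close to neutral, or it reverses.

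**The case against.** The best defence is that the protocol speaks of one worst on-treatment value, in the singular, and gives no any-visit rule. Elsewhere both documents sort individual results simply into low, normal or high. Choosing a single worst value is therefore a possible reading of the protocol. That stands in part, and it means the any-visit rule is a repair and not a restoration of text. It does not rescue the SAP, because a single value cannot be both low and high: on this reading the fourth category has no meaning, yet both documents name it.

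It is also fair to say that no data are lost. SAP 15.1.6 lists all laboratory data flagged against the normal ranges, SAP 15.3 lists out-of-range values from scheduled and unscheduled visits, and SAP 15.1.1 adds minimum and maximum to the by-visit summaries. With about 15 children and no hypothesis tests, a reader can go through the listings child by child. This limits the harm, but a listing is not the tabulated summary that was specified.

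Finally, an any-visit flag treats a trivial excursion like a severe one, and at t = 10% it would put nearly half the children in the combined category. That is a real cost, though a small one beside a category that cannot be used.

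**Conclusion.** Wrong as written. The SAP's rule contradicts the classification that it is meant to implement, the scale it depends on is undefined, and the departure is not declared in SAP 4.3. The category mismatch and the dependence on scale follow from the text and simple arithmetic. Only the counts in step 3 rest on assumptions (t, equal tails and independent visits). At n = 15 one child is 1/15 = 6.7 percentage points of a table; that is a unit of measurement, not an expected effect.

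The scope is narrow: this shift table, tests without CTCAE v4.03 grades, and children abnormal in both directions. The documents do not say which tests are ungraded, so the number affected cannot be stated. A child with low values only is still shown as Low.

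A reader might go further and infer that the rule favours High and systematically hides low shifts, because in raw units a non-negative result cannot fall below LLN by more than LLN itself. The documents do not support that. The SAP does not say that deviations are in raw units, and step 4 shows that the favoured direction varies with the scale and the test's distribution. The rule can hide a high shift just as well.

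**What to change.** Replace the sub-bullet in SAP 15.1.6 with a rule over all post-baseline values, unscheduled visits included:

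- Low: at least one value below LLN and none above ULN
- High: at least one value above ULN and none below LLN
- Low and high: at least one of each
- Normal: otherwise

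Then tabulate against baseline. This makes all four categories reachable, removes the need for a deviation scale or a tie rule, and uses data already collected. The cost is one SAP edit and simple programming. The flags ignore the size of an excursion, which remains visible in the listings and, less directly, in the by-visit minimum and maximum.

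If a single direction per child is really intended, the alternative is to define the scale and a tie rule, drop the fourth category from both documents, and record the change in SAP 4.3.

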15.2 Deaths

If any patients die during the study the information will be presented in a summary table and a data listing.

15.3 Laboratory Evaluations

Results from the local laboratory will be included in the reporting of this study for Hematology, Blood Chemistry, Virus Serology, Troponin, Coagulation Panel, Urinalysis, Electrocardiogram, and Echocardiogram. A list of laboratory assessments to be included in the outputs is included in the protocol section 8.4.1 Laboratory evaluations.

Central laboratory evaluation will be included in the reporting of this study for anti-AAV9 Ab

Presentations will use SI Units. If necessary, laboratory conversion will be applied.

Quantitative laboratory measurements reported as below the lower limit of quantification (BLQ), will be represented as the lower limit value; measurements reported as above the upper limit of quantification (ULQ), will be converted to the higher limit value for the purpose of quantitative summaries, but will be presented as recorded, i.e. as "< X" or "> X"> in the listings.

[figure not shown]
Note: handling of retests and unscheduled measurements are included in Section 7 to save repetition in different sections of the SAP.

The following summaries will be provided for laboratory data:

Change from baseline by visit (for quantitative measurements) (only scheduled visits)

Document: Document path and title

Template No.: RWI_TP_BIOS0013 Revision 2 Reference: RWI_WI_BIOS0015

- Incidence of abnormal values according to normal range criteria that resulted in an adverse event (according to CTCAE grading), considering scheduled and unscheduled visit assessments.
- Shift from baseline by visit according to Common Toxicity (CTC) grading system, if applicable, considering scheduled and unscheduled visit assessments.
- Patients meeting elevation criteria for liver function test based on laboratory data by weight bracket and overall (considering scheduled and unscheduled visit assessments) (ALT > 2 x ULN; ALT > 3 x ULN; ALT > 5 x ULN; ALT > 10 x ULN; ALT > 20 x ULN; AST > 2 x ULN; AST > 3 x ULN; AST > 5 x ULN; AST > 10 x ULN; AST > 20 x ULN; ALT or AST > 2 x ULN;; ALT or AST > 5 x ULN; ALT or AST > 8 x ULN; ALT or AST > 10 x ULN; ALT or AST > 20 x ULN; Total bilirubin > 2 x ULN; Total bilirubin > 3 x ULN; ALT or AST > 3 x ULN and Total bilirubin > 2 x ULN and ALP < 2 x ULN)

- Time until hepatotoxicity since baseline (considering scheduled and unscheduled visit assessments)
- Time until cardiac event since baseline (considering scheduled and unscheduled visit assessments)
- Frequency of hepatotoxicity (considering scheduled and unscheduled visit assessments)
- Frequency of cardiac event (considering scheduled and unscheduled visit assessments)
- Listing of laboratory data outside the normal range (considering scheduled and unscheduled visit assessments)

15.3.1 Laboratory Specific Derivations

Liver event:

Alanine aminotransferase (ALT) or aspartate aminotransferase (AST) > 3 x ULN

Document: Document path and title

Template No.: RWI_TP_BIOS0013 Revision 2 Reference: RWI_WI_BIOS0015

Total bilirubin (TBL) >1.5 x ULN

Cardiac event:

Presence of clinically relevant finding on ECG and/or Echocardiogram

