6.2 Other treatment(s)

In accordance to this protocol, all study participants will receive immunomodulatory therapy with prednisolone. Immunomodulatory therapy is intended to mitigate safety risks associated with immune response to the AAV9 capsid that may occur after administration of OAV101. Immune responses may lead to elevations in liver transaminases or elevations of Troponin I. Where feasible, the participant's vaccination schedule should be adjusted to accommodate concomitant corticosteroid administration prior to and following OAV101. In addition to consideration for corticosteroids, vaccinations should be withheld 2 weeks pre and 4 weeks post OAV101 administration. Prior to initiation of the immunomodulatory regimen and prior to administration of OAV101, the participant must be checked for symptoms of active infectious disease of any nature.

Starting 24 hours prior to infusion of OAV101, it is required to initiate an immunomodulatory regimen with corticosteroids following the schedule below.

Table 6-2 Pre and post-infusion corticosteroid use

Pre-infusion	24 hours prior to OAV101 infusion	Prednisolone orally 1 mg/kg/day or equivalent
Post-infusion	At least 30 days (including the day of OAV101 administration)	Prednisolone orally 1 mg/kg/day or equivalent
Tapering	Once liver function tests return to baseline or after Day 30 if no liver function test elevation observed	decrease dose by 0.25 mg/kg per week

Prednisolone treatment of 1 mg/kg/day will be continued post-infusion until liver function tests return to baseline.

Protocol No. COAV101A1IC01

Page 29 of 66

For participants that require steroid dosing longer than 60 days total (including the weaning period) Pediatric GI/hepatology specialty evaluation will be considered to address the risk of opportunistic infections and to make recommendations for infectious prophylaxis.

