8.4.2 Electrocardiogram (ECG)

8.4.2.1 12-Lead electrocardiogram

A 12-lead ECG will be performed at times indicated in the Schedule of Assessments.

In the case of a series of assessments, ECG should be the first assessment obtained while participant is at rest. The preferred sequence of cardiovascular data collection during study visits is ECG collection first, followed by vital signs, and blood sampling.

During feasibility, the ECG readout availability should be confirmed at the site for QTcF. If a site only has availability to readout in QTcB (Bazett) and NOT QTcF, the ECG machine must still be able to provide QT and RR interval values so the Investigator can perform the below QTcF (Fridericia) calculation to determine eligibility. The Fridericia QT correction formula (QTcF) must be used for clinical decisions.

Unless auto calculated by the ECG machine, the Investigator must calculate QTcF at the Screening and/or Baseline visit(s) (as applicable) to assess eligibility according to the following formula:

$$QTcF = rac{QT}{\sqrt[3]{RR}}$$

Triplicate 12-lead ECGs are to be collected with ECG machines available at the site. Each ECG tracing must be labeled with study number, participant initials, Participant No., date and time, and filed in the study site source documents. The Investigator should document clinical evaluation in the source documents.

The ECG will be interpreted locally by a pediatric cardiologist or designee for immediate safety evaluation. If the participant is hemodynamically compromised, the Investigator or a medically qualified person must initiate appropriate safety procedures without delay.

Additional, unscheduled, safety ECGs may be repeated at the discretion of the Investigator at any time during the study as clinically indicated. A

Clinically significant ECG findings at baseline must be discussed with Novartis before administration of study treatment.

Clinically significant abnormalities must be recorded on the relevant section of the medical history/Current medical conditions/AE eCRF as appropriate.

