7.2 Baseline

Baseline is defined as the last non-missing measurements taken prior to reference start date (including unscheduled assessments) and after the study enrollment.

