	Notalgia paraesthetica [10072643]
	Pain [10033371]
	Pain threshold decreased [10066956]
	Paradoxical pain [10067055]
	Paraesthesia [10033775]
	Peripheral nervous system function test abnormal [10034591]
	Peripheral sensorimotor neuropathy [10056673]
	Peripheral sensory neuropathy [10034620]
	Radicular pain [10059604]

Document: Document path and title

Template No.: RWI_TP_BIOS0013 Revision 2 Reference: RWI_WI_BIOS0015

AESI	Search methodology (MedDRA version 25.0 or later) [MedDRA	
	Code]	
	Reflex test abnormal [10068273]	
	Reflexes abnormal [10038254]	
	Reversed hot-cold sensation [10073738]	
	Sensorimotor disorder [10062162]	
	Sensory disturbance [10040026]	
	Sensory ganglionitis [10066196]	
	Sensory integrative dysfunction [10048871]	
	Sensory level abnormal [10061567]	
	Sensory loss [10040030]	
	Skin burning sensation [10054786]	
	Slow response to stimuli [10041045]	
	Synaesthesia [10078814]	
	Temperature perception test decreased [10068015]	
	Tenderness [10043224]	
	Thermoanaesthesia [10068010]	
	Thermohypoaesthesia [10068009]	
	Tinel's sign [10052492]	
	Trichodynia [10079852]	
	Unresponsive to stimuli [10045555]	
	Vibratory sense increased [10068327]	

AESI: Adverse event of special interest; HLT: High Level Terms; PT: Preferred Terms; SMQ: Standardized MedDRA Queries

See Appendix 2 for handling of partial dates for AEs. In the case where it is not possible to define an AE as treatment emergent or not, the AE will be classified by the worst case; i.e. treatment emergent.

Document: Document path and title

Template No.: RWI_TP_BIOS0013 Revision 2 Reference: RWI_WI_BIOS0015

Page 23 of 45

The incidence of TEAEs and AESIs will be summarized. Descriptive summary statistics for the change from baseline in cardiac safety assessments (ECG, Echocardiogram, troponin), clinical laboratory measurements (including hematology and liver function assessments), and vital signs will be summarized descriptively by visit/timepoint. A summary of all laboratorial assessments (including scheduled and unscheduled visits) will be summarized separately. Mean, standard deviation, median, minimum, and maximum will be presented for continuous variables. Categorical data will be presented as frequencies and percentages. For each applicable visit/timepoint, only participants with a baseline and a measurement for that timepoint will be included in the summary.

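### The SAP's derived cardiac event need not be new, worse or post-infusion, and its time origin is not the infusion and is not fixed

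*SAP*

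**What the plan says.** SAP 15.3.1 (Laboratory Specific Derivations) gives the whole definition of a cardiac event in one line: "Presence of clinically relevant finding on ECG and/or Echocardiogram". SAP 15.3 (Laboratory Evaluations) builds two summaries on it: "Frequency of cardiac event (considering scheduled and unscheduled visit assessments") and "Time until cardiac event since baseline (considering scheduled and unscheduled visit assessments").

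Three other SAP provisions bear on this. SAP 7.1 makes the dosing day, Day 1, the reference start date. SAP 7.2 says: "Baseline is defined as the last non-missing measurements taken prior to reference start date (including unscheduled assessments) and after the study enrollment". SAP 7.4, Table 1, separately lists a visit named Baseline at Day -1.

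Protocol Table 8-1 schedules the ECG at Screening Visit 1 and again at the Baseline visit. The only scheduled echocardiogram before dosing is at Screening Visit 1. On ECG findings before dosing, Protocol 8.4.2.1 says: "Clinically significant ECG findings at baseline must be discussed with Novartis before administration of study treatment".

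**The concern.** A safety event derived after a one-time gene therapy should describe what appeared or worsened after the infusion. The SAP applies that rule to adverse events: SAP 15.1.1 counts an event as treatment-emergent only if it began or worsened on or after dosing. SAP section 7 also separates a pre-treatment from an on-treatment period. Neither restriction is attached to the cardiac event in 15.3.1. A child with a relevant ECG or echocardiogram finding before dosing, and the same finding afterwards, meets the definition.

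The time summary has a related weakness. Its clock starts at baseline, although the SAP has defined the infusion day as its reference date, and the SAP does not say which date baseline means for an event drawn from two kinds of assessment. Two programmers could derive different times from the same data. Cardiac adverse events are a listed important risk in the protocol and cardiac safety assessments belong to the primary objective, so readers will look at these two tables.

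**Working it through.** The plan gives no figure for this event. Its only computable design figure is in Protocol 12.7.1, and it reproduces: with a true rate of 14% and 15 children, 1 - 0.86^15 = 0.896, stated as approximately 90%. Nothing below depends on it except the sample size of about 15.

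**Inputs**

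- Screening Visit 1: Day -20 with a window of +5, so Day -20 to Day -15 (Protocol Table 8-1; SAP Table 1).
- Baseline visit: Day -1. Infusion: Day 1. Neither table has a Day 0.
- Last scheduled ECG before dosing: Day -1. Only scheduled echocardiogram before dosing: Day -20 to Day -15.
- First scheduled ECG and echocardiogram after dosing: Week 1, nominally Day 8.

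**Time origin.** With no Day 0, the interval from a negative day to a positive day is (later - earlier - 1).

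Distance between the two baselines under SAP 7.2: from -1 - (-15) = 14 days to -1 - (-20) = 19 days.

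A finding seen on Day 8 is then timed as follows:

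| Origin | Calculation | Days |
|---|---|---|
| Infusion, Day 1 | 8 - 1 | 7 |
| Day -1 (the ECG's own baseline, or the Baseline visit) | 8 + 1 - 1 | 8 |
| Echocardiogram's own baseline, latest (Day -15) | 8 + 15 - 1 | 22 |
| Echocardiogram's own baseline, earliest (Day -20) | 8 + 20 - 1 | 27 |

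If each assessment keeps its own baseline, the same Day 8 visit gives 8 days by ECG and 22 to 27 days by echocardiogram. The longest is 27/7 = 3.9 times the time since infusion. If baseline means the Day -1 visit for both, the gap between them is 0 and both give 8 days. An unscheduled echocardiogram before dosing would shorten the gap on the first reading, because SAP 7.2 admits unscheduled assessments.

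**Frequency.** With 15 children, each child counted only for an unchanged pre-dose finding adds 1/15 = 6.7 percentage points. The documents give no prevalence of such findings. As an assumption only, for prevalence p the chance of at least one such child among 15 is 1 - (1 - p)^15:

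- p = 5%: 1 - 0.95^15 = 54%
- p = 10%: 1 - 0.90^15 = 79%
- p = 20%: 1 - 0.80^15 = 96%

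These show how the problem scales. They are not estimates for this population.

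**The case against.** The strongest reply is that this touches little. Treatment-emergent events keep their began-or-worsened rule, and the cardiac events of special interest come from a separate MedDRA search (SAP Table 2) that does not use the 15.3.1 derivation. Protocol 12.4.2 and 12.4.8 contain no derived cardiac event, and no test or decision rule depends on one. All of this stands and limits the point to two descriptive summaries.

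It can also be said that few pre-existing findings will enter. Exclusion 15 names cardiomyopathy among clinically significant unstable conditions, and Protocol 8.4.2.1 asks for discussion of a significant baseline ECG finding; it does not say that dosing then goes ahead. That is fair, and it is why no count is given. But a required discussion is not an exclusion, so a stable finding can enter, and the definition has no provision for it.

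Three stronger readings are tempting, and the documents do not support them:

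- **That ECG and echocardiogram events are in fact timed from origins up to 19 days apart.** The SAP never says so. The gap follows from one reading of baseline and is zero on the other. What is established is that the origin is not fixed. The output templates might settle it, but SAP Appendix 3 shows no content in the public version.
- **That pre-existing findings would be reported as drug effects.** The two summaries give a frequency and a time and attribute no cause.
- **That a troponin-only signal would be missed because troponin is not in the definition.** SAP 15.1.1 summarises "change from baseline in cardiac safety assessments (ECG, Echocardiogram, troponin") by visit, and SAP 15.3 lists laboratory values outside the normal range from scheduled and unscheduled visits. The protocol does name troponin as a possible immune signal ("Immune responses may lead to elevations in liver transaminases or elevations of Troponin I"), but limiting this derived event to ECG and echocardiogram findings while reporting troponin separately is a defensible choice.

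**Conclusion.** The point holds for the definition and for the time origin. Followed literally, SAP 15.3.1 counts an unchanged pre-dose finding as a cardiac event, at 6.7 percentage points per child if 15 are treated. How many children this affects cannot be derived, so the frequency can be inflated but is not shown to be. The time to event starts before the infusion on either reading of baseline. The excess is 1 day if the origin is Day -1. For an echocardiogram finding timed from its own scheduled baseline it is 15 to 20 days (22 - 7 to 27 - 7).

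This rests on the schedule in Protocol Table 8-1, on no unscheduled echocardiogram before dosing, and on no clarification in output templates that are not public. The change is worth making, but the main adverse event analyses do not depend on it.

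**What to change.** In SAP 15.3.1, define a cardiac event as a clinically relevant ECG or echocardiogram finding after the OAV101 infusion that was absent at, or is worse than, that child's last pre-dose assessment of the same type. State how a child with no pre-dose assessment of that type is handled. In SAP 15.3, measure time to the event from the reference start date (Day 1, SAP 7.1) for both assessments. Troponin can stay in its existing summaries and listing.

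The cost is SAP wording and derivation code. The assessments are already scheduled, and no visit or clinical procedure changes. The one added task is to decide in advance what counts as worse on each assessment. SAP 5.1 carries the final-analysis derivations into the interim analyses unless stated otherwise, so the change should be made before any of these tables is produced.
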